Achilles Pain Block

NCT 03316378

Date of Document: 4/29/19

[figure not shown]
Date study protocol initially approved by the IRB: 1/27/2016

Date study was most recently approved by the IRB: 8/13/2018

Study design

In this mechanistic, non-randomized controlled trial, all participants repeated testing twice in the following order within a single laboratory-based testing session: 1) pain-rating with activity, 2) movement analysis during high- and low-level tasks, 3) pain psychology questionnaires; 4) quantitative sensory testing (See figure below). The only difference in procedure between groups was that the AT group received an anesthetic injection after the first set of tests. For participants with bilateral AT the more painful side was designated the involved side for testing and injection. A sports medicine physician used sonographic guidance to inject 4 mL of 0.5% ropivacaine superficial and deep to the tendon to ensure coverage of the painful region. This dose was chosen based on clinical experience of the amount of ropivacaine needed to numb the area for minimally-invasive outpatient procedures. To minimize the risk of infection sterile technique was used, including sterile gloves, area of injection scrubbed, sterile gel, and a sterile transducer cover. The onset for ropivacaine was 10-20 minutes and pain relief lasted for 6-8 hours. Repeat testing began 30 minutes after the injection. Participants with AT were contacted 1-day and 1-week following testing to ask about any injection-related adverse events (e.g. increased pain, infection). All participants were contacted 1-week after testing to complete the pain catastrophizing scale (PCS).

Figure 1. All participants completed two sets of testing. The group with Achilles tendinopathy pain received a local anesthetic injection prior to repeat testing. The control group without Achilles tendinopathy pain did not receive an injection prior to the second set of testing.

Statistical Analysis

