A priori power analysis determined that a sample size of 20 per group was needed to detect effect sizes (between groups ≥ 0.91 , between repeat tests ≥ 0.68) less than or equal to published results for ankle power (mean difference = 0.9 W/kg, SD = 0.9 W/kg)¹, kinesiophobia (minimal detectable change = 5.6, SD = 5.7)², and pressure pain threshold (group difference = 171.8 kPa, SD = 174.8 kPa)³ with a power $\geq 80\%$ and statistical significance defined as $P \leq 0.05$ (**Table 1**). Because 3 participants with AT had insufficient pain relief from the

anesthetic injection, an additional 3 participants were recruited per group to ensure adequate power, resulting in a final sample size of 46. Sample characteristics were compared between groups using independent samples t-test for parametric data, Mann-Whitney U test for non-parametric data, or Chi-square test for categorical data. Changes in Achilles tendon pain from pre-injection to post-injection were compared with Wilcoxon Signed Ranks tests. Mixed effects ANOVAs were used to examine the effects of group, time, and a group*time interaction for motor performance, pain psychology, and quantitative sensory testing. The type I error rate for the ANOVAs was maintained at 0.05 by using Bonferroni adjustment for multiple comparisons (3 tests for motor performance, 2 tests for pain psychology, 3 tests for quantitative sensory testing). Post-hoc comparisons were performed to examine significant interaction effects and p-values were adjusted using a Bonferroni adjustment for the number of time points compared (2 for TSK, 3 for PCS, 4 for quantitative sensory test). Pearson correlations examined relationships between the magnitude of change with an anesthetic injection of identified indicators of altered central processing in the AT group.

Primary outcome / dependent variable	Assumed SD	Detectable difference	Published difference
Specific Aim 1.1, n=40, between groups, detectable effect size ≥ 0.91			
PPT (Central sensitization)	174.8 kPa ³	158.9 kPa	171.8 kPa ³
TSK (Psychological factor)	5.7 ²	5.2	MDC= 5.6 ²
Ankle power (Motor control)	0.9 W/kg ¹	0.8 W/kg	0.9 W/kg ¹
Specific Aim 1.2, n=20, repeated measures, detectable effect size ≥ 0.68			
PPT (Central sensitization)	28%	19%	25.8% ⁴
TSK (Psychological factor)	5.7 ²	3.8	MDC= 5.6 ²
Ankle power (Motor control)	0.9 W/kg ¹	0.6 W/kg	0.9 W/kg ¹

References

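### Table 1's Aim 1.2 detectable differences reproduce as an AT-only paired t-test at unadjusted 0.05, not as the Bonferroni-adjusted group-by-time analysis the plan describes

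*Combined protocol and SAP*

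**What the plan says.** The Aim 1.2 block of Table 1 is headed "Specific Aim 1.2, n=20, repeated measures, detectable effect size ≥ 0.68". It lists an assumed SD, a detectable difference and a published difference for each outcome: 28%, 19% and 25.8% for PPT; 5.7, 3.8 and an MDC of 5.6 for TSK; 0.9, 0.6 and 0.9 W/kg for ankle power. The Statistical Analysis text attaches power of at least 80% and a 0.05 significance level, and mentions no multiplicity adjustment in the power calculation.

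The same section then describes the analysis: "Mixed effects ANOVAs were used to examine the effects of group, time, and a group*time interaction". It adds that "The type I error rate for the ANOVAs was maintained at 0.05 by using Bonferroni adjustment for multiple comparisons", with counts of "3 tests for motor performance, 2 tests for pain psychology, 3 tests for quantitative sensory testing". On the follow-up tests it says "Post-hoc comparisons were performed to examine significant interaction effects", with adjustment factors of "2 for TSK, 3 for PCS, 4 for quantitative sensory test". No factor is listed for motor performance.

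On the design, the Study design section says "The only difference in procedure between groups was that the AT group received an anesthetic injection after the first set of tests". Both groups repeat the whole test battery.

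**The concern.** The power line and the analysis text describe different tests. An n of 20 is one group, while the mixed ANOVA uses both. The power line uses 0.05, while the ANOVAs use 0.05/3 for PPT and ankle power and 0.05/2 for TSK. The documents do not say which ANOVA term answers Aim 1.2. The interaction is the natural candidate: both groups are retested and only the AT group is injected, so it is the term that separates the injection from repeat testing.

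A second gap is that Table 1 does not say whether its Aim 1.2 SDs are SDs of change. For TSK and ankle power it reuses the Aim 1.1 SDs; the power text gives "ankle power (mean difference = 0.9 W/kg, SD = 0.9 W/kg" for ankle power without reference to change.

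Table 1 is the only statement of what pre/post change the trial could detect. A reader weighing a null interaction would credit it with 80% power at 19%, 3.8 points or 0.6 W/kg, and the documents do not support that.

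**Working it through.** **Inputs.** Differences, SDs, n and alpha are from Table 1 and the Statistical Analysis text. The number analysed is not fixed by the text: 46 were recruited, 23 per group, after three AT participants had insufficient relief. Cases are therefore written AT/control as 20/20, 20/23 and 23/23. Assumptions added here: zero mean change in controls, and a single pre/post contrast with 1 df. The plan counts 4 time points for QST without defining them, so the PPT test may differ. All power figures are two-sided, from the noncentral t unless noted.

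**1. The plan's own figure.** Paired t: df = 19, noncentrality = d√n = 0.68 × √20 = 3.04, critical value 2.093. Power is 82.2%, and 80% is reached at d = 0.660. The table's differences give 19/28 = 0.679, 3.8/5.7 = 0.667 and 0.6/0.9 = 0.667, with power 82%, 81% and 81%. As a check on alpha and sidedness, Aim 1.1 (d = 0.91, 20 per group) gives 80.1% at unadjusted two-sided 0.05. The arithmetic is right for that test.

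**2. Interaction at the stated differences, table SDs taken as SDs of change.** With two time points this is a two-sample t-test on change scores: df = n1 + n2 − 2, noncentrality = d/√(1/n1 + 1/n2). For PPT at 20/20: 0.679 × 3.162 = 2.15 against a critical value of 2.505 at alpha 0.0167, giving 37%. The halved-SD columns come from simulating the pooled test (200,000 runs).

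| Outcome (alpha) | Equal SDs 20/20 | 20/23 | 23/23 | Control SD halved 20/20 | 23/23 |
|---|---|---|---|---|---|
| PPT (0.0167) | 37% | 40% | 43% | 59% | 66% |
| TSK (0.025) | 42% | 45% | 48% | 63% | 70% |
| Ankle power (0.0167) | 36% | 39% | 42% | 57% | 64% |

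At unadjusted 0.05 and 20/20 with equal SDs, power is still only 55%, 54% and 54%.

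**3. AT-only paired contrast, n = 20, at the plan's post-hoc alpha.** PPT at 19%: 61%, if the factor of 4 means 0.05/4 = 0.0125. TSK at 3.8: 71% at 0.05/2 = 0.025. Ankle power at 0.6 W/kg: 81%, because no factor is listed, though the text ties post-hoc tests to a significant interaction.

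**4. If the SDs are raw-score SDs.** SD of change = SD × √(2(1 − r)), which equals the SD only at a pre/post correlation of 0.5. With equal change SDs, the r that gives 80% at the stated difference is 1 − ½(d/d80)², where d80 is the detectable effect in step 6. For PPT at 20/20: 1 − ½(0.679/1.064)² = 0.80. From 23/23 to 20/20 the requirement is 0.76–0.80 (PPT), 0.75–0.78 (TSK) and 0.77–0.80 (ankle power). At r = 0.8, power is 81%, 84% and 79% (20/20) or 87%, 89% and 86% (23/23).

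**5. Interaction at the published differences, Bonferroni alpha, equal change SDs.**

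| Outcome | 20/20 | 20/23 | 23/23 |
|---|---|---|---|
| PPT, 25.8% | 65.9% | 69.6% | 73.5% |
| TSK, 5.6 | 77.7% | 80.9% | 84.0% |
| Ankle power, 0.9 W/kg | 74.2% | 77.7% | 81.2% |

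With the control change SD halved, the range over all outcomes and sample sizes is 87–97%. On the paired reading at post-hoc alpha with n = 20, PPT has 90% and TSK 97%.

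**6. What the interaction could detect at 80% (table SDs as equal change SDs).** At 20/20, d80 is 1.064 (alpha 0.0167) and 1.009 (0.025). At 23/23 it is 0.987 and 0.936. Multiplying by the SDs gives 29.8%, 5.7 points and 0.96 W/kg (20/20), or 27.6%, 5.3 and 0.89 (23/23). Relative to the printed 0.68 the ratios run from 0.936/0.68 = 1.38 to 1.064/0.68 = 1.56. Relative to the exact 80% threshold of 0.660 they run from 1.42 to 1.61.

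**The case against.** The strongest reply is that nothing is miscalculated. Table 1 marks Aim 1.2 as a repeated-measures comparison with n of 20, against n of 40 for Aim 1.1, so the row already signals one group. Tying Aim 1.2 to the interaction is an inference, because the documents do not define the aim. That stands, and it makes this a mismatch between planning and analysis, not an arithmetic error. It does not rescue the whole block: on the one-group reading, the plan's own post-hoc factors still leave PPT and TSK below 80% at the stated differences.

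A reader might infer that the stated differences can be met by no test except the unadjusted paired one. The documents do not support that. If the SDs are raw-score SDs and the pre/post correlation is near 0.8, the interaction at Bonferroni alpha also gets there. The plan states no correlation, so the case can be neither claimed nor excluded.

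Equal change SDs are also an assumption. Controls have no tendon pain and no injection, so their changes may vary less. Halving their SD raises power at the stated differences to about 57–70%, which narrows the gap without closing it.

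The PPT row is the least secure. Its SD and difference are percentages, so 28% may already be an SD of percent change, and step 4 would then not apply to it.

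**Conclusion.** The point holds for the stated detectable differences. The Aim 1.2 line is correct for an AT-only paired t-test at unadjusted two-sided 0.05, and the plan describes no such test. With table SDs as SDs of change and no mean change in controls, the interaction has 36–48% power at those differences (equal change SDs) or about 57–70% (control SD halved). The paired reading at post-hoc alpha gives 61% for PPT and 71% for TSK, and only ankle power keeps its 81%.

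A reader might go further and conclude that the trial was underpowered. The documents do not show that. At the published differences, interaction power is 66–84% with equal change SDs and 87–97% with the control SD halved, and the paired reading gives 90% for PPT and 97% for TSK. Which case applies depends on the ANOVA term, the kind of SD, the correlation, the control variability and the number analysed, none of which is stated. Confidence is high that the power line and the analysis do not match, and moderate on the size of the gap.

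**What to change.** Keep the Aim 1.2 rows as the a priori record and label them as AT-only paired comparisons at unadjusted two-sided 0.05. In the Statistical Analysis text:

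- Name the ANOVA term that answers Aim 1.2, and give the post-hoc factor for motor performance or say there is none.
- State whether the assumed SDs are SDs of change and, if not, the pre/post correlation.
- State the number analysed, including whether the three AT participants with insufficient relief are in.
- Restate the detectable differences at the Bonferroni alpha actually used. If the term is the interaction, the step 6 figures (29.8%, 5.7 points and 0.96 W/kg at 20/20; 27.6%, 5.3 and 0.89 at 23/23) can serve as a sensitivity line, shown with their assumptions: table SDs as equal change SDs, and controls unchanged on average.

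The cost is one label, a few table entries and two or three sentences. Sample size and analysis do not change. The downside is a less favourable stated sensitivity, and the added figures are retrospective and should be marked so.
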